3.6 Exploratory Endpoints

- Platelet count assessments and platelet response during the Extension Phase.
- Subject reported palatability and parent/caregiver reported acceptability assessed by a palatability/acceptability questionnaire administered after the first dose of the powder for oral suspension.

4 STUDY DESCRIPTION

4.1 Summary of Study Design

AVA-PED-301 is a multi-center, randomized, double-blind, placebo-controlled, parallel-group study in pediatric subjects with a 12 week Core Phase followed by an open-label Extension Phase to evaluate the efficacy, safety, tolerability, and PK/PD profile of avatrombopag, as well as provide data on palatability/acceptability, dosing parameters, and response to treatment.

The study will enroll at least 72 pediatric subjects, aged ≥1 to <18 years (Figure 1). Subjects will be assigned to 3 age cohorts in a 2:2:1 ratio and subjects will be randomized within each cohort in a 3:1 ratio to receive either avatrombopag or placebo. Subject age at the time of randomization will be used. Cohort 1 and Cohort 2 will each enroll more subjects than will be enrolled in Cohort 3 in order to minimize the exposure of the youngest age group to placebo.

Enrollment into the Core Phase will be staggered by descending age cohort.

- Cohort 1: \ge 12 to <18 years (n = 21 avatrombopag; 7 placebo)
- Cohort 2: \geq 6 to <12 years (n = 21 avatrombopag; 7 placebo)
- Cohort 3: ≥ 1 to ≤ 6 years (n = 12 avatrombopag; 4 placebo)

[figure not shown]

Figure 1 AVA-PED-301 Study Design

All available PK and safety data through Week 10 of the study will be reviewed by the Sponsor and/or the Sponsor's designee (e.g., for unblinded PK data) for the first 10 subjects enrolled into Cohort 1 prior to opening enrollment into the Core Phase for subjects in Cohort 2. Likewise, all available PK and safety data through Week 10 will be reviewed by the Sponsor and/or the Sponsor's designee (e.g., for unblinded PK data) for the first 10 subjects enrolled into Cohort 2, prior to opening enrollment into the Core Phase for Cohort 3. As the study progresses and more data become available, the PK/PD model will be updated with emerging data in order to confirm the appropriate dose of avatrombopag in each cohort. Enrollment will not stop in the current cohort for the data review after Week 10, or for the data review after each cohort is fully enrolled.

The dose of avatrombopag may be modified during the study based on results of the PK and safety data review. In addition, safety data will be reviewed on an ongoing basis and new enrollment may be paused for any serious unexpected and related AEs that occur (Figure 2).

[figure not shown]

Figure 2 AVA-PED-301 Enrollment and Data Review Plan

PK = pharmacokinetic; PD = pharmacodynamic

Enrollment will not stop in the current cohort for the data review after Week 10, or for the data review after each cohort is fully enrolled.

Subjects who are not showing a platelet response (i.e., a lack of treatment effect) at the highest dose of study drug based on the subject's age cohort may be terminated from the Core Phase and directly enrolled into the open-label Extension Phase (Section 5.3).

Lack of treatment effect will be defined as:

- Platelet count remains <30×10⁹/L after more than 3 weeks at the maximum dose of study drug per Table 4. Subjects may also be terminated from the Core Phase and directly enrolled into the Extension Phase after 7 days of therapy at the maximum dose if they have dangerously low platelet counts (in the opinion of the Investigator), or
- Subjects who require rescue therapy more than 3 times or continuous rescue therapy for more than 3 weeks (Section 8.6).

[figure not shown]
4.1.1 Core Phase

The Core Phase of AVA-PED-301 is designed to assess the efficacy, safety, and tolerability of avatrombopag in pediatric subjects with ITP.

In order to participate in the Core Phase of the study, informed consent/assent must be completed by the subject and/or the subject's Legally Authorized Representative (LAR).

Subjects who participate in the Core Phase will enter a Screening Period followed by a 12 week Treatment Period after which they may either complete the study with an End of Study Visit that will occur 30 days after the last dose of study drug or continue into the open-label Extension Phase. The Core Phase of the study will last 12 weeks (approximately 84 days), which does not include the 4 week Follow-up Period, with study visits occurring once weekly through the end of Week 12 (Figure 3).

Figure 3 AVA-PED-301: Core Phase Study Schematic

4.1.1.1 Screening Period

The Screening Visit (Visit 1) will be completed within 28 days prior to Baseline (Day 1/Visit 2).

4.1.1.2 Treatment Period (Visit 2 Through Visit 14)

Enrollment will begin with Cohort 1 (ages ≥ 12 to < 18 years). Enrollment into Cohort 2 (ages ≥ 6 to < 12 years) and Cohort 3 (ages ≥ 1 to < 6 years) will begin after notification from the Sponsor as described in Section 4.1 and Figure 2. Subject age at the time of randomization will be used.

At Day 1/Visit 2 eligible subjects will be randomized 3:1 to receive either avatrombopag or placebo at the starting dose determined by the PK/PD modeling described in Section 1.1.5. Throughout the Treatment Period, the dose of avatrombopag may be titrated up or down by the Investigator, based on platelet count (Table 4).

Subjects may be removed from the Core Phase and directly enrolled into the open-label Extension Phase due to a lack of treatment effect (Section 5.3).

Blood samples for serial PK assessments will be collected during Visit 4 (Week 2) and Visit 12 (Week 10) of the Core Phase. During these visits, subjects ≥6 years of age will have a blood sample drawn pre-dose and between 2 to 4 hours, 6 to 8 hours, and 10 to 12 hours post-dose (4 samples drawn at each visit, 2 mL each). Subjects <6 years of age will have a blood sample drawn pre-dose and at 2 to 4 hours post-dose but will be randomized in a 1:1 ratio, stratified by treatment group, to either the 6 to 8 hour or the 10 to 12 hour post-dose timepoint at Visit 4 (Week 2). The timepoint not drawn at Visit 4 (Week 2) will be drawn at Visit 12 (Week 10) (3 samples drawn at each visit, 2 mL each). For all age groups, blood samples for sparse PK assessments (2 mL each) will be collected while the subject is at the clinic during Visit 3 (Week 1) and at each visit during Visit 5 to Visit 11 (Week 3 to Week 9; 8 samples, 2 mL each) (Section 9.6).

After Visit 14 (Week 12), the subject may enter the 2-year open-label Extension Phase (Section 9.2). If the subject does not enter the Extension Phase, an End of Study Visit (Section 9.1.16) must be completed approximately 30 days after the last dose of study drug, prior to discharging the subject from the study. Visit 14 will serve as the last visit of the Core Phase and the first visit of the Extension Phase (Visit E-1).

4.1.1.3 End of Study Visit (for Subjects *not* Continuing into the Extension Phase)

Subjects who are not continuing into the 2-year open-label Extension Phase will be followed for 30 days (± 7 days) following the last dose of study drug in the Core Phase. Once the End of Study Visit (Section 9.1.16; Table 7) has been completed, the subject may be discharged from the study.

4.1.2 Extension Phase

Subjects who complete the 12 week Core Phase of the study, or who meet the stopping criteria as defined in Section 5.3 and are discontinued from the Core Phase, will be eligible to enter the open-label Extension Phase, if they continue to meet the inclusion criteria and do not meet any exclusion criteria for this phase of the study. Subjects and/or the subject's LAR must complete informed consent/assent in order to participate in the Extension Phase of the study.

Until the last subject completes the Core Phase and the database is locked, the Sponsor, all subjects, and all Investigators will remain blinded to treatment received in the Core Phase. Dosing of openlabel avatrombopag during the Extension Phase is described in Section 1.1.6.

Study visits will begin with Visit E-1/Month 1 which will be the same day as Visit 14 in the Core Phase. After dosing with open-label avatrombopag has been initiated during Visit E-1/Day 1, the subject should have weekly platelet counts drawn until it is determined that the subject is receiving a stable dose of avatrombopag. Otherwise, during the Extension Phase, visits will occur every 30 days for 24 months through Visit E-24/Month 24 (Figure 4).

Figure 4 AVA-PED-301: Extension Phase Study Schematic

4.1.2.1 End of Study Visit

9.1.20; Table 8) has been completed, the subject may be discharged from the study.

5 PHARMACOKINETIC AND SAFETY DATA REVIEW

5.1 Ongoing Data Review

All available PK and safety data through Week 10 of the study will be reviewed by the Sponsor and/or the Sponsor's designee (e.g., for unblinded PK data) for the first 10 subjects enrolled into Cohort 1 prior to opening enrollment into the Core Phase for subjects in Cohort 2. Likewise, all available PK and safety data through Week 10 will be reviewed by the Sponsor and/or the Sponsor's designee (e.g., for unblinded PK data) for the first 10 subjects enrolled into Cohort 2, prior to opening enrollment into the Core Phase for Cohort 3. Enrollment will not stop during this data review period.

As the study progresses and data become available, the pediatric PK/PD model will be updated with emerging data in order to confirm the appropriate dose of avatrombopag in each cohort. The PK/PD model will be updated after each age cohort is fully enrolled, but without stopping enrollment for remaining cohorts. The dose of avatrombopag may be modified during the study based on results of the PK and safety data review.

Safety data will be reviewed on an ongoing basis and new enrollment may be paused for any serious unexpected and related AEs that occur (Figure 2).

The exact doses of avatrombopag may be modified during the study based on PK/PD analysis of emerging PK/PD and safety data.

The Sponsor and the project team will remain blinded during the ongoing safety data review. Interim PK/PD analyses will be conducted by an unblinded designee.

5.2 Independent Data Monitoring Committee

An Independent Data Monitoring Committee (IDMC) will assess the overall status of the study and the safety of subjects. An IDMC charter will be developed to govern IDMC activities which will pre-specify the rules for safety reporting and safety analyses to be presented to the IDMC. The IDMC will make formal recommendations about the conduct of the study and safety of study participants following each IDMC meeting.

In general, it is anticipated that the IDMC will be asked to perform a safety review in the case of thromboembolic events or serious unexpected adverse reactions occurring in ≥ 2 subjects in any single Cohort in the Core Phase.

5.3 Stopping Criteria

Subjects may be removed from the Core Phase and directly enrolled into the open-label Extension Phase due to a lack of treatment effect.

A lack of treatment effect will be defined as:

- Platelet count remains <30×10⁹/L after more than 3 weeks at the maximum dose of study drug per Table 4. Subjects may also be terminated from the Core Phase and directly enrolled into the Extension Phase after 7 days of therapy at the maximum dose if they have dangerously low platelet counts (in the opinion of the Investigator), or
- Subjects who require rescue therapy more than 3 times or continuous rescue therapy for more than 3 weeks (Section 8.6).

6 SELECTION AND EARLY TERMINATION OF SUBJECTS

The following criteria for enrollment must be met to be eligible for the study. The Investigator or other study site personnel must document in the source documents that the informed consent form (ICF) and/or assent form, as required by the Institutional Review Board (IRB)/Independent Ethics Committee (IEC), was signed and dated prior to any study procedures being performed. The date informed consent/assent was obtained will also be recorded in the eCRF.

6.1 Inclusion and Exclusion Criteria for the Core Phase

6.1.1 Inclusion Criteria

Subjects who meet all of the following criteria will be eligible to participate:

- 1. Male or female subjects ≥ 1 and ≤ 18 years of age at Screening and Baseline.
- 2. Subject and/or subject's LAR must be able to provide informed consent and/or assent, as applicable.
- 3. Subject has a confirmed diagnosis of primary ITP according to the International Consensus Report on the Investigation and Management of Primary ITP (Provan, 2019) for ≥6 months duration and has had an insufficient response to a previous treatment, in the opinion of the Investigator.
- 4. Subject has an average of 2 platelet counts $<30\times10^9/L$ with no single count $>35\times10^9/L$.
 - The platelet count obtained at the Screening Visit/Visit 1 and 1 other platelet count taken within 28 days on either side of the Screening Visit (may use a historical value collected per standard of care if within 28 days of Screening) will be averaged to obtain the study eligibility platelet count value, which must be $<30\times10^9$ /L. The 2 samples must be obtained ≥24 hours and ≤28 days apart and the results must be available prior to randomization.
- 5. Subjects being treated chronically with corticosteroids or azathioprine/6-mercaptopurine must be receiving a stable dose for at least 30 days prior to Day 1/Visit 2 or must have completed these therapies more than 30 days prior to Day 1/Visit 2.
- 6. Subjects being treated with mycophenolate mofetil (MMF), cyclosporine (CsA), sirolimus, or danazol must be receiving a stable dose for at least 90 days prior to Day 1/Visit 2 or must have completed these therapies more than 30 days prior to Day 1/Visit 2.
- 7. Previous therapy for ITP with immunoglobulins (IVIg and anti-D) or corticosteroid rescue therapy must have been completed at least 14 days prior to Day 1/Visit 2.
- 8. Cyclophosphamide and vinca alkaloid regimens must have been completed at least 30 days prior to Day 1/Visit 2.
- 9. Splenectomy and rituximab must have been completed at least 90 days prior to Day 1/Visit 2.
- 10. Previous therapy with any other TPO-RAs (e.g., eltrombopag or romiplostim) or recombinant human TPO must have been completed 28 days prior to Day 1/Visit 2.
- 11. Previous therapy with vitamin K antagonists, antifibrinolytic agents, recombinant activated factor VII, heparin, factor Xa inhibitors, direct thrombin inhibitors, desmopressin, or chronic antiplatelet therapy must have been completed within 7 days of Day 1/Visit 2.

- 12. Previous therapy with moderate or strong dual inducers or moderate or strong dual inhibitors of CYP2C9 and CYP3A4 must have been completed within 7 days of Day1/Visit 2 (Appendix D).
- 13. Platelet transfusion, or receipt of blood products containing platelets must have been completed within 7 days of Day 1/Visit 2. Packed red blood cells (RBCs) are permitted.
- 14. Females of childbearing potential must have a negative urine or serum pregnancy test at Screening and Day 1/Visit 2 and must not be breastfeeding.
- 15. Female subjects of childbearing potential and who are sexually active and male subjects who are sexually active must agree to use highly effective methods of contraception.
- 16. Subject and/or subject's LAR is willing and able to comply with all aspects of the protocol.

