- 3. Subject has a confirmed diagnosis of primary ITP according to the International Consensus Report on the Investigation and Management of Primary ITP (Provan, 2019) for ≥6 months duration and has had an insufficient response to a previous treatment, in the opinion of the Investigator.
- 4. Subject has an average of 2 platelet counts $<30\times10^9/L$ with no single count $>35\times10^9/L$.
 - The platelet count obtained at the Screening Visit/Visit 1 and 1 other platelet count taken within 28 days on either side of the Screening Visit (may use a historical value collected per standard of care if within 28 days of Screening) will be averaged to obtain the study eligibility platelet count value, which must be $<30\times10^9$ /L. The 2 samples must be obtained ≥24 hours and ≤28 days apart and the results must be available prior to randomization.
- 5. Subjects being treated chronically with corticosteroids or azathioprine/6-mercaptopurine must be receiving a stable dose for at least 30 days prior to Day 1/Visit 2 or must have completed these therapies more than 30 days prior to Day 1/Visit 2.
- 6. Subjects being treated with mycophenolate mofetil (MMF), cyclosporine (CsA), sirolimus, or danazol must be receiving a stable dose for at least 90 days prior to Day 1/Visit 2 or must have completed these therapies more than 30 days prior to Day 1/Visit 2.
- 7. Previous therapy for ITP with immunoglobulins (IVIg and anti-D) or corticosteroid rescue therapy must have been completed at least 14 days prior to Day 1/Visit 2.
- 8. Cyclophosphamide and vinca alkaloid regimens must have been completed at least 30 days prior to Day 1/Visit 2.
- 9. Splenectomy and rituximab must have been completed at least 90 days prior to Day 1/Visit 2.
- 10. Previous therapy with any other TPO-RAs (e.g., eltrombopag or romiplostim) or recombinant human TPO must have been completed 28 days prior to Day 1/Visit 2.
- 11. Previous therapy with vitamin K antagonists, antifibrinolytic agents, recombinant activated factor VII, heparin, factor Xa inhibitors, direct thrombin inhibitors, desmopressin, or chronic antiplatelet therapy must have been completed within 7 days of Day 1/Visit 2.
- 12. Previous therapy with moderate or strong dual inducers or moderate or strong dual inhibitors of cytochrome P450 (CYP)2C9 and CYP3A4 must have been completed within 7 days of Day1/Visit 2.

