8.5 Prohibited Medications and/or Procedures

The following medications and/or procedures are prohibited:

- Immunoglobulins (IVIg and anti-D) are prohibited during the study unless needed as a rescue therapy (Section 8.6). Immunoglobulins must have been completed at least 14 days prior to Day 1/Visit 2.
- Platelet transfusion, or receipt of blood products containing platelets, within 7 days of Day 1/Visit 2 and during the study unless needed as a rescue therapy (Section 8.6). Packed RBCs are permitted.
- Cyclophosphamide and vinca alkaloid regimens must have been completed at least 30 days prior to Day 1/Visit 2.
- Splenectomy and rituximab must have been completed at least 90 days prior to Day 1/Visit 2.
- Use of other TPO-RAs (e.g., eltrombopag or romiplostim) or recombinant human TPO within 28 days prior to Day 1/Visit 2 and during the study.
- Use of vitamin K antagonists, antifibrinolytic agents, recombinant activated factor VII, heparin, factor Xa inhibitors, direct thrombin inhibitors, desmopressin, or chronic antiplatelet therapy (>30 days) during the study.
- Previous therapy with moderate or strong dual inducers or moderate or strong dual inhibitors of CYP2C9 and CYP3A4 must have been completed within 7 days of Day 1/Visit 2 (Appendix D).
- Enrollment in another clinical study with any investigational drug or device within 30 days of Screening or during the study; however, participation in observational studies within the previous 30 days is permitted.

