8.6 Rescue Therapies

Subjects may receive rescue therapy at the discretion of the Investigator if there is an urgent need to increase platelet count, such as in the case of life-threatening thrombocytopenia, in the opinion of the Investigator, clinical signs and symptoms suggesting a potential bleed (e.g., wet purpura) or a major bleed. All rescue medications, including dose and frequency, must be recorded on the eCRF.

Rescue therapy may include:

- The addition of any *new* ITP medication or medication to treat thrombocytopenia, such as:
 - Corticosteroids
 - o IVIg
 - o Anti-D
 - Platelet transfusion
- Any *increase in the Day 1/Visit 2 dose* of a concomitant ITP medication.
- TPO-RAs are not allowed as rescue therapy.

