9.1.2 Screening (Visit 1/Day -28 to -1)

The Screening Visit must be completed within 28 days of Day 1/Visit 2.

The following procedures will be performed at the Screening Visit.

- Collect signed and dated informed consent/assent prior to any study procedures.
- Review of inclusion/exclusion criteria (Section 6.1) to confirm study eligibility.
- Record subject demographic information.
- Record medical/medication/surgical history to include all past significant illnesses and/or surgeries (in the opinion of the Investigator) and all medications taken (including non-prescription medications, vitamins, dietary supplements, and herbal products) within the past 90 days.
- Record ITP history, including date of diagnosis and any concomitant ITP medications.
- Collect height and weight to determine BMI (calculated by eCRF).
- Perform abbreviated physical exam (PE). The abbreviated PE will consist of the following: general appearance, head, neck, eyes, ears, nose, throat, chest, lungs, heart, abdomen, extremities, joints, lymph nodes, and neurology.
- Collect vital signs (blood pressure, heart rate, and temperature). Vital signs should be taken after sitting for 5 minutes, whenever possible, and prior to any blood draws.
- Collect blood for clinical laboratory tests to assess study eligibility as outlined in Section 6 (see details in Section 9.5 and Core Phase Schedule of Events, Table 7).
 - Local laboratories may be used to confirm study eligibility, however, for study analysis and reporting purposes, only values determined at a central laboratory will be used with the exception of platelet count (Section 9.5).
- Collect blood for platelet count (local laboratory).

- o The platelet count obtained at the Screening Visit/Visit 1 and 1 other platelet count taken within 28 days on either side of the Screening Visit (may use a historical value collected per standard of care if within 28 days of Screening) will be averaged to obtain the study eligibility platelet count value, which must be <30×10⁹/L. The 2 samples must be obtained ≥24 hours and ≤28 days apart and the results must be available prior to randomization.
- Perform urine or serum pregnancy test for female subjects of childbearing potential. The pregnancy test may be performed locally.
- Review and record AEs that may have occurred after signing informed consent/assent.
- Discharge subject from clinic with instructions for when to return for Day 1/Visit 2.

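### Inclusion criteria 11 to 13 set a 7-day maximum where a 7-day minimum washout is meant; criterion 13 then contradicts Section 8.5

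*Protocol*

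**What the plan says.** Three Core Phase inclusion criteria share one timing phrase.

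- Criterion 11, on drugs that act on clotting (Protocol 6.1.1, repeated in the Synopsis): "direct thrombin inhibitors, desmopressin, or chronic antiplatelet therapy must have been completed within 7 days of Day 1/Visit 2".
- Criterion 12, on dual CYP2C9/CYP3A4 inducers and inhibitors: "dual inhibitors of CYP2C9 and CYP3A4 must have been completed within 7 days of Day1/Visit 2 (Appendix D" in Section 6.1.1, and "dual inhibitors of cytochrome P450 (CYP)2C9 and CYP3A4 must have been completed within 7 days of Day1/Visit 2" in the Synopsis.
- Criterion 13, on platelet transfusion (Section 6.1.1, repeated in the Synopsis): "Platelet transfusion, or receipt of blood products containing platelets must have been completed within 7 days of Day 1/Visit 2".

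Section 8.5 lists prohibited treatments. It bars transfusion of "blood products containing platelets, within 7 days of Day 1/Visit 2 and during the study unless needed as a rescue therapy (Section 8.6". For the criterion 11 drugs it bars use of "direct thrombin inhibitors, desmopressin, or chronic antiplatelet therapy (>30 days) during the study" and gives no interval before Day 1. For the criterion 12 drugs it repeats the criterion's own phrase.

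The neighbouring washouts are worded differently. Criteria 7 to 9 give a minimum number of days before Day 1, and criteria 5 and 6 ask for completion more than 30 days before. Neither the amendment log (Protocol Appendix E) nor the SAP clarifies the 7-day intervals.

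**The concern.** A requirement that something be completed within N days of a date sets an upper limit on the gap. The protocol uses the form that way itself in Section 9.1.2: "The Screening Visit must be completed within 28 days of Day 1/Visit 2". Criteria 11 to 13 therefore ask for recent exposure where they should exclude it. The same preposition points the right way in a prohibition, such as the transfusion bullet in Section 8.5, but is reversed once the sentence becomes a requirement to have finished.

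Subjects must meet every criterion, so this is operative text. Four things could be affected:

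- **Consistency of eligibility decisions** across sites.
- **Safety.** Literal criterion 11 admits a child with a mean count below 30×10⁹/L who stopped an anticoagulant the day before Day 1.
- **Early platelet counts and PK samples.** The Day 8 response is a secondary endpoint, and PK sampling starts at Visit 3.
- **Per-protocol membership.** This is only possible, because SAP 6.6 leaves the exclusion criteria to a separate document and the PPS analysis is supportive.

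**Working it through.** The plan has no figure to reproduce here. The check is a comparison of texts, followed by simple day counting.

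**1. Where the phrase occurs.** Three criteria × two places (Synopsis and Section 6.1.1) = 6, plus the CYP bullet in Section 8.5 = 7.

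**2. Criterion 13 against Section 8.5.** Let k be the whole days from the last transfusion to Day 1.

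| Is day 7 'within 7 days'? | Literal criterion 13 allows | Section 8.5 allows (no rescue exception) | Days in common |
|---|---|---|---|
| Yes | k = 0 to 7 | k ≥ 8 | none |
| No | k = 0 to 6 | k ≥ 7 | none |

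A transfusion 3 days before Day 1 meets criterion 13 and breaches Section 8.5. One 20 days before does the reverse.

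The rescue exception does not remove the conflict. Section 8.6 begins "Subjects may receive rescue therapy at the discretion of the Investigator if there is an urgent need to increase platelet count" and counts increases from the Day 1 dose, so it describes children already in the study. If it were stretched to the days before Day 1, a rescue transfusion at k = 0 to 7 would satisfy both texts. One at k ≥ 8 would still fail literal criterion 13.

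**3. Criteria 11 and 12.** A last dose the day before Day 1 satisfies the literal wording. Of the eight bullets in Section 8.5, six state the direction of the pre-study restriction clearly: immunoglobulins, transfusion, cyclophosphamide/vinca alkaloids, splenectomy/rituximab, TPO-RAs and other studies. The two that do not are the bullets for these drugs.

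**4. How old an admitted transfusion would be.** Age at a visit on day d is d − 1 + k. Visit windows are ±1 day (Protocol 9.1.4, 9.1.5 and 9.1.8).

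| Visit | Day d | Literal criterion 13 (k = 0 to 7) | Youngest with k ≥ 7 |
|---|---|---|---|
| Visit 3 (Week 1) | 7 to 9 | 6 + 0 = 6 to 8 + 7 = 15 days | 6 + 7 = 13 |
| Visit 4 (Week 2, earliest serial PK) | 14 to 16 | 13 + 0 = 13 to 15 + 7 = 22 days | 13 + 7 = 20 |
| Visit 7 (Week 5) | 35 to 37 | 34 + 0 = 34 to 36 + 7 = 43 days | 34 + 7 = 41 |

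Protocol Section 1.1 gives a platelet lifespan of 7 to 10 days in healthy people. Against the 10-day end, an admitted transfusion is still within the lifespan only at Visit 3, and only for k = 0 to 4 (visit on Day 7), 0 to 3 (Day 8) or 0 to 2 (Day 9). Section 1.2 notes increased platelet destruction in ITP, so carry-over is less likely still.

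The documents give no offset times for the CYP drugs, so an effect on early PK is possible but not shown.

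**The case against.** The strongest reply is that no sensible reader would apply the literal text.

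- Read literally, criterion 13 would exclude a child whose only transfusion was months ago. Yet SAP 7.3.2 plans to summarise the time in weeks from the last transfusion to first dose, which fits a minimum washout better.
- Criteria 5 to 9 are plainly washout or stable-dose rules, and Section 8.5 is headed as a list of prohibitions.
- Exclusion 16 uses similar wording for a barred window.
- For transfusions, Section 8.5 states the right rule anyway.
- Exclusion 3 (any thrombosis history) and exclusion 17 (investigator judgement) reduce the chance of enrolling a recently anticoagulated child.
- SAP 4.1 counts screening as a study period, so a ban during the study arguably starts at consent.
- Protocol 13.3 puts every amendment through full review, at about 50 sites.

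Much of this stands. The intent can be inferred, and the practical consequence is small. But the same evidence shows that a 7-day minimum was meant, which confirms that the written rule runs the wrong way. The exclusions make the safety example rarer without setting an interval. The SAP 4.1 reading sets none either: screening may fall as late as Day −1, so a ban from consent could begin one day before dosing. For criteria 11 and 12 a site can reach 7 days only by analogy. On cost, Amendment 2 already reworded criteria 5 and 7 to clarify washouts, so the sponsor has treated such wording as worth correcting.

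**Conclusion.** The concern holds. Criteria 11 to 13 and the CYP bullet in Section 8.5 state a maximum interval where a minimum was intended. Criterion 13 as written contradicts Section 8.5, and no section gives a clear minimum washout for the drugs in criteria 11 and 12.

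The error is one of drafting, with limited reach. Any platelet carry-over would be confined to the Visit 3 count, on the assumption that transfused platelets last no longer than the 10 days quoted for healthy people. The primary endpoint, power and alpha are untouched. The number of children affected is not given, and nothing in the documents shows that a site misapplied the text. It is worth correcting because following the eligibility text as written gives wrong decisions and the remedy is nearly free.

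**What to change.** In criteria 11, 12 and 13, in both the Synopsis and Section 6.1.1, and in the CYP bullet of Section 8.5, replace 'within 7 days of' with 'at least 7 days prior to' Day 1/Visit 2. Criteria 7 to 9 already use this form.

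Reword the Section 8.5 transfusion bullet at the same time, to bar transfusion less than 7 days before Day 1/Visit 2. Otherwise the two passages may differ on one day: a minimum of 7 days allows k = 7, while the present bullet bars k = 7 if day 7 counts as within 7 days. The documents do not say whether it does.

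Alternatively, use 'more than 7 days prior to' in criterion 13 and leave the transfusion bullet unchanged. The two then agree only if day 7 counts as within the window, so the first option is cleaner.

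The cost is eight wording edits (7 + 1), or seven with the alternative, by clarification letter or in the next amendment. Design, sample size and analysis do not change.
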